6.4 STUDY INTERVENTION/EXPERIMENTAL MANIPULATION ADHERENCE

Participation in all three sessions (MRI and two stimulation sessions) is mandatory for participants to remain active participants in the study. Participation will be tracked across sessions by a single ID number associated with all data collected across the three sessions. All study components will be completed within one of the three sessions, so there is no issue of adherence beyond those three sessions.

6.5 CONCOMITANT THERAPY

N/A

6.5.1 RESCUE THERAPY

N/A

7 STUDY INTERVENTION/EXPERIMENTAL MANIPULATION DISCONTINUATION AND PARTICIPANT DISCONTINUATION/WITHDRAWAL

7.1 DISCONTINUATION OF STUDY INTERVENTION/EXPERIMENTAL MANIPULATION

Reasons for discontinuation of a stimulation (TMS) session include discomfort or expressed desire to discontinue a TMS session. Some individuals receiving TMS, for example, have reported headaches associated with stimulation and may request discontinuation.

When a subject discontinues from a TMS session, and a clinically significant finding is identified after enrollment, the investigator will determine if any change in participant management is needed. Any new clinically relevant finding will be reported as an adverse event (AE).

The data to be collected at the time of study intervention discontinuation will include the following:

- The reason(s) for discontinuing the participant from the intervention

7.2 PARTICIPANT DISCONTINUATION/WITHDRAWAL FROM THE STUDY

Participants are free to withdraw from participation in the study at any time upon request.

An investigator may discontinue a participant from the study for the following reasons:

- Identification of brain abnormalities during the MRI scan
- Non-compliance with regards to cognitive task instructions
- Lost-to-follow up; unable to contact subject (see **Section 7.3, Lost to Follow-Up**)
- Any event or medical condition or situation occurs such that continued collection of follow-up study data would not be in the best interest of the participant or might require an additional treatment that would confound the interpretation of the study; With TMS an unlikely but possible medical condition would be onset of a seizure
- The participant meets an exclusion criterion (either newly developed or not previously recognized) that precludes further study participation

The reason for participant discontinuation or withdrawal from the study will be recorded on the Case Report Form (CRF). Subjects who sign the informed consent form and are randomized but do not receive the study intervention may be replaced. Subjects who sign the informed consent form, and are randomized and receive the study intervention, and subsequently withdraw, or are discontinued from the study, will be replaced.

7.3 LOST TO FOLLOW-UP

A participant will be considered lost to follow-up if he or she fails to appear for the MRI session, or appear or return for two scheduled stimulation sessions and study staff are unable to contact the participant after at least 3 attempts.

The following actions must be taken if a participant fails to return for a required study visit:

- The site will attempt to contact the participant, reschedule the missed visit within one week, counsel the participant on the importance of maintaining the assigned visit schedule and ascertain if the participant wishes to and/or should continue in the study
- Before a participant is deemed lost to follow-up, the investigator or designee will make every effort to regain contact with the participant (3 emails). These contact attempts will be documented in the participant's medical record or study file.
- Should the participant continue to be unreachable, he or she will be considered to have withdrawn from the study with a primary reason of lost to follow-up

8 STUDY ASSESSMENTS AND PROCEDURES

8.1 ENDPOINT AND OTHER NON-SAFETY ASSESSMENTS

During the screening process, participants will be informed about basic inclusion / exclusion criteria after they first contact us, by email. We will then ask participants questions, by phone, on the MRI and TMS screening forms in detail and indicate whether they meet criteria or not. Although we will not yet ask participants to fill out these forms (i.e. no data will be recorded at this stage), we will ask them to confirm

that they meet all criteria on the forms, prior to scheduling their first visit. Within two weeks of this confirmation, we will invite participants for their first session visit.

At the first visit, participants will complete the informed consent process and then be asked to fill out the screening forms, after giving consent. These data will include information about psychiatric or psychological history, presence or absence of metal in the body, history of physical trauma to the brain, current alcohol or drug abuse, current use of psychoactive medications, and use of other medications which may lower the seizure threshold. We will also collect basic demographic and handedness information.

Following the informed consent process the following data will be collected during the study

- **Performance-based assessments:** Working memory task performance, decision-making task performance
- **Questionnaires:** The Need for Cognition Scale
- **Imaging assessments:** Using a 64-channel EEG system, we will record brain waves at the scalp throughout all procedures during the stimulation session. In the MRI scanner we will collect several types of scans. For the purposes of TMS neuro-navigation, we will collect T1 MPRAGE sequences, structural localizer scans, and a field map scan. We will also collect 10-12 minutes of resting state fMRI data. These data will be collected on a 3T MRI.

8.2 SAFETY ASSESSMENTS

N/A

8.3 ADVERSE EVENTS AND SERIOUS ADVERSE EVENTS

8.3.1 DEFINITION OF ADVERSE EVENTS

This protocol uses the definition of adverse event from 21 CFR 312.32 (a): any untoward medical occurrence associated with the use of an intervention in humans, ***whether or not considered intervention-related.***

8.3.2 DEFINITION OF SERIOUS ADVERSE EVENTS

Any adverse event that (i) results in death; (ii) is life-threatening (places the subject at immediate risk of death from the event as it occurred); (iii) results in inpatient hospitalization or prolongation of existing hospitalization; (iv) results in persistent or significant disability/incapacity; (v) results in congenital anomaly/birth defect; or (vi) based upon appropriate medical judgement, may jeopardize the subject's health and may require medical or surgical intervention to prevent one of the other outcomes listed in this definition.

8.3.3 CLASSIFICATION OF AN ADVERSE EVENT

8.3.3.1 SEVERITY OF EVENT

For adverse events (AEs) not included in the protocol defined grading system, the following guidelines will be used to describe severity.

- **Mild** – Events require minimal or no treatment and do not interfere with the participant's daily activities.
- **Moderate** – Events result in a low level of inconvenience or concern with the therapeutic measures. Moderate events may cause some interference with functioning.
- **Severe** – Events interrupt a participant's usual daily activity and may require systemic drug therapy or other treatment. Severe events are usually potentially life-threatening or incapacitating. Of note, the term "severe" does not necessarily equate to "serious".

8.3.3.2 RELATIONSHIP TO STUDY INTERVENTION/EXPERIMENTAL MANIPULATION

All adverse events (AEs) will have their relationship to study procedures, including the intervention, assessed by an appropriately-trained clinician based on temporal relationship and his/her clinical judgment. The degree of certainty about causality will be graded using the categories below.

- **Related** – The AE is known to occur with the study procedures, there is a reasonable possibility that the study procedures caused the AE, or there is a temporal relationship between the study procedures and the event. Reasonable possibility means that there is evidence to suggest a causal relationship between the study procedures and the AE.
- **Not Related** – There is not a reasonable possibility that the study procedures caused the event, there is no temporal relationship between the study procedures and event onset, or an alternate etiology has been established.

8.3.3.3 EXPECTEDNESS

A clinician with appropriate expertise in transcranial magnetic stimulation will be responsible for determining whether an adverse event (AE) is expected or unexpected. An AE will be considered unexpected if the nature, severity, or frequency of the event is not consistent with the risk information previously described for the study procedures.

8.3.4 TIME PERIOD AND FREQUENCY FOR EVENT ASSESSMENT AND FOLLOW-UP

The occurrence of an adverse event (AE) or serious adverse event (SAE) may come to the attention of study personnel during study visits and interviews of a study participant presenting for medical care, or upon review by a study monitor.

All AEs, not otherwise precluded per the protocol, will be captured on the appropriate case report form (CRF). Information to be collected includes event description, time of onset, clinician's assessment of severity, relationship to study procedures (assessed only by those with the training and authority to make a diagnosis), and time of resolution/stabilization of the event. All AEs occurring while on study will be documented appropriately regardless of relationship. All AEs will be followed to adequate resolution.

Any medical or psychiatric condition that is present at the time that the participant is screened will be considered as baseline and not reported as an AE. However, if the study participant's condition deteriorates at any time during the study, it will be recorded as an AE.

Changes in the severity of an AE will be documented to allow an assessment of the duration of the event at each level of severity to be performed. Documentation of onset and duration of each episode will be maintained for AEs characterized as intermittent.

The Principal Investigator will record events with start dates occurring any time after informed consent is obtained until 7 (for non-serious AEs) or 30 days (for SAEs) after the last day of study participation. At each study visit, the investigator will inquire about the occurrence of AE/SAEs since the last visit. Events will be followed for outcome information until resolution or stabilization.

8.3.5 ADVERSE EVENT REPORTING

Reportable Events

Principal Investigators must report to Brown's HRPP the occurrence of any of the events described below, collectively referred to as Reportable Events:

- Any Adverse Event (AE) that (1) is a UAE and (2) is related or possibly related to participation in the research.
- Any UP.
- Any breach of Privacy or Confidentiality, including lost or stolen confidential information of a research participant.
- Any medical, procedural, or laboratory error potentially increasing risk to participants (e.g., errors in drug administration or dosing, surgical or other procedures, testing of samples, or test results).
- Any interim analysis, safety monitoring report, publication in a peer-reviewed journal, or other finding indicating that there are new or increased risks to subjects or others, or that subjects are less likely to receive any direct benefits from the research study than as initially presented to the IRB or HRPP.
- Any complaint by or on behalf of a subject indicating that the rights, welfare, or safety of the subject have been adversely affected.
- Any change in the Food and Drug Administration (FDA) labeling; any change in the status of an Investigational New Drug Application (IND) or Investigational Device Exemption (IDE); any withdrawal from market; any manufacturer alert from the sponsor of the research study; or any recall of an FDA-approved drug, device, or biologic under investigation in the research study.
- Any event that requires prompt reporting to the sponsor of the research study, when applicable.
- A Suspension or Termination of a research study or of a study's enrollment, including by the FDA or the sponsor of the research study, based on information indicating that the research study places subjects at an increased risk of harm than was previously known or recognized.
- Any other event that is unanticipated (irrespective of any "relatedness" to the research) and indicates that the research study places subjects or others (e.g., other investigators, research assistants, students, the public, family members or partners of subjects) at an increased risk of harm or otherwise adversely affects the rights, welfare, or safety of subjects or others.

Reporting Timeframes

Principal Investigators must report Reportable Events to the HRPP in accordance with the following timeframes:

- Reportable Events that are either life-threatening or have resulted in death must be reported to the HRPP via telephone, or email if phone is not possible, within one business day from the date the PI is notified of or discovers the Reportable Event. The PI must ensure that Research Personnel are trained to report any Reportable Event to the PI promptly upon discovery, and no later than

24 hours following its discovery or occurrence. A Reportable Events Form must be submitted to the HRPP within 48 hours of the PI's initial verbal or email notification to the HRPP of the Reportable Event.

- Reportable Events that are not life-threatening and have not resulted in death must be reported to the HRPP in writing as soon as possible, and no later than 7 business days from the date the PI is notified of or discovers the Reportable Event.
- Minor Protocol Deviations must be reported to the HRPP in writing at the time of continuing review when continuing review is applicable to the study protocol, and must be reported during any quality assurance/quality improvement assessment by the HRPP. If continuing review is not applicable to the study protocol, the PI must maintain Minor Protocol Deviations as part of the study record and make the study record available upon request to the IRB, HRPP, and/or any federal sponsor or regulatory agency, as applicable.

Reporting Reportable Events

In accordance with the timeframes outlined above, PIs must submit to the HRPP a Reportable Events Form and include the following information:

- Identifying information for the research study, including the study title, the PI's name, and the IRB protocol number;
- A detailed description of the Reportable Event, including relevant dates and times;
- A detailed description of any corrective action or change to the protocol, planned or already taken, to ensure that the Reportable Event is corrected and will not occur again;
- An assessment of whether any research participants or others were placed at risk as a result of the Reportable Event, or suffered any physical, social, or psychological harm and any plan to address these consequences; and
- Any other information deemed relevant by the PI

8.3.6 SERIOUS ADVERSE EVENT REPORTING

The PI will be responsible for conducting an evaluation of a serious adverse event and shall report the results of such evaluation to the NIH and the reviewing Institutional Review Board (IRB) as soon as possible, but in no event later than 7 working days after the event.

8.3.7 REPORTING EVENTS TO PARTICIPANTS

Incidental findings related to the structural MRI scans are possible. MRIs are collected by the Brown MRF (Magnetic Resonance Facility) and staff MD who will review the images for any reportable anomalies and contact participants directly if any are identified.

8.3.8 EVENTS OF SPECIAL INTEREST

N/A

8.3.9 REPORTING OF PREGNANCY

If participants indicate during screening that there is a chance they may be pregnant, we supply and ask participants to take a pregnancy test to ensure that they are not pregnant. If they are pregnant they will be withdrawn from the study and all procedures (MRI, TMS) for safety reasons.

8.4 UNANTICIPATED PROBLEMS

8.4.1 DEFINITION OF UNANTICIPATED PROBLEMS

This protocol uses the definition of Unanticipated Problems as defined by the Office for Human Research Protections (OHRP). OHRP considers unanticipated problems involving risks to participants or others to include, in general, any incident, experience, or outcome that meets all of the following criteria:

- Unexpected in terms of nature, severity, or frequency given (a) the research procedures that are described in the protocol-related documents, such as the Institutional Review Board (IRB)-approved research protocol and informed consent document; and (b) the characteristics of the participant population being studied;
- Related or possibly related to participation in the research (“possibly related” means there is a reasonable possibility that the incident, experience, or outcome may have been caused by the procedures involved in the research); and
- Suggests that the research places participants or others at a greater risk of harm (including physical, psychological, economic, or social harm) than was previously known or recognized.

UPs may warrant corrective actions. Examples of corrective actions or changes that might need to be considered in response to an UP include:

- Modification of inclusion or exclusion criteria to mitigate the newly identified risks
- Implementation of additional safety monitoring procedures
- Suspension of consenting/enrollment of new participants or halting of study procedures for consented/enrolled participants
- Modification of informed consent documents to include a description of newly recognized risks
- Provision of additional information about newly recognized risks to previously consented/enrolled participants.

8.4.2 UNANTICIPATED PROBLEMS REPORTING

The principal investigator (PI) will report unanticipated problems (UPs) to the reviewing Institutional Review Board (IRB). The UP report will include the following information:

- Protocol identifying information: protocol title and number, PI's name, and the IRB project number
- A detailed description of the event, incident, experience, or outcome
- An explanation of the basis for determining that the event, incident, experience, or outcome represents an UP
- A description of any changes to the protocol or other corrective actions that have been taken or are proposed in response to the UP

To satisfy the requirement for prompt reporting, UPs will be reported using the following timeline:

- UPs that are serious adverse events (SAEs) will be reported to the IRB and to the DCC/study sponsor/funding agency within 1 business day of the investigator becoming aware of the event
- Any other UP will be reported to the IRB and to the DCC/study sponsor/funding agency within 7 business days of the investigator becoming aware of the problem
- All UPs should be reported to appropriate institutional officials (as required by an institution's written reporting procedures), the supporting agency head (or designee), and the Office for Human Research Protections (OHRP) within one month of the IRB's receipt of the report of the problem from the investigator

8.4.3 REPORTING UNANTICIPATED PROBLEMS TO PARTICIPANTS

For UPs that impact on all participants, all participants will be notified within two weeks, in writing, of the UP and corrective actions which have been taken.

9 STATISTICAL CONSIDERATIONS

There will not be a formal Statistical Analysis Plan (SAP). Also, no statistical plan will be posted publicly or registered before the study begins.

9.1 STATISTICAL HYPOTHESES

- Primary Endpoint(s):

We predict that, relative to pre-stimulation rest, continuous theta burst stimulation (cTBS) will result in a reduction of the local balance of cortical excitation to inhibition as reflected in the functional E/I balance in proximity to stimulated targets.

We also predict that, relative to pre-stimulation rest, cTBS will result in a reduction in markers of critical dynamics (including, e.g., long-range temporal correlations) in proximity to stimulation targets.

Finally, we predict that, relative to angular gyrus stimulation, cTBS to the dorsolateral prefrontal cortex will increase subjective cognitive effort.

- Secondary Endpoint(s):

We hypothesize that subjective effort reflects divergence from a critical state and that criticality depends on the E/I balance. As such, we predict that there will be individual difference correlations in the degree to which TMS perturbs E/I balance, alters measures of criticality including long-range temporal correlations, and ultimately amplifies subjective effort.

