3 OBJECTIVES AND ENDPOINTS

OBJECTIVES	ENDPOINTS	JUSTIFICATION FOR ENDPOINTS	PUTATIVE MECHANISMS OF ACTION
Primary			
Test whether continuous theta-bursts stimulation induces sub-critical dynamics in the cortex	Diminished markers of critical dynamics include reduced long-range temporal correlations measured by detrended fluctuation analysis, and sub-critical avalanche branching ratios.	Long-range temporal correlations and avalanche branching dynamics are widely used metrics of distance from the critical point (degree of sub-criticality) in EEG studies.	Long-range temporal correlations and avalanche branching ratios of 1.0 are emergent properties of dynamical systems at a critical point. By reducing the E/I balance, continuous theta burst stimulation should make the brain more sub-critical, thus dampening these emergent properties.
Test whether continuous theta-bursts stimulation to dlPFC diminishes working memory function relative to stimulation to the angular gyrus.	Lower discrimination (d') accuracy and slower reaction times on the N-back following dlPFC stimulation.	Criticality affords dynamic flexibility as needed for rapid, reliable updating in the N-back task, and also flexible task switching. Prior work has shown that dlPFC continuous theta burst can undermine working memory function. Here we test the specific hypothesis that this reflects the effects	A decrease in the E/I balance in the dlPFC produced by dlPFC theta-burst stimulation should make the brain more sub-critical, thus impairing functional flexibility afforded by a critical state. This should matter most

OBJECTIVES	ENDPOINTS	JUSTIFICATION FOR ENDPOINTS	PUTATIVE MECHANISMS OF ACTION
		of TMS-induced sub-criticality in the dlPFC.	in the dlPFC which is a key nexus of higher-order working memory function.
Test whether continuous theta burst stimulation to the dlPFC increases subjective cognitive effort relative to stimulation to the angular gyrus.	Steeper discounting of rewards contingent on the expenditure of cognitive effort following dlPFC stimulation versus angular gyrus stimulation.	By virtue of dlPFC's involvement in working memory and cognitive control, it is hypothesized to play a key role in subjective cognitive effort. We specifically predict that critical dynamics in the dlPFC are what the brain tracks as subjective effort.	
Secondary			

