Test whether continuous theta-burst stimulation decreases E/I balance	Decrease in the functional E/I (fE/I) balance ratio at rest, estimated from EEG data after TMS	The fE/I measure derived from EEG activity has been shown to index E/I balance in silico, and in vivo with humans taking GABAergic medication. Thus, in principle, a change in E/I balance induced by TMS should also be apparent in the EEG dynamics and thereby the fE/I of channels near the stimulation site. Changes in fE/I should moderate effects of theta-burst stimulation on critical dynamics and	Theta-burst stimulation is thought to promote inhibitory neurotransmission, at diverse timescales, thus decreasing E/I balance in local microcircuits. The fE/I measure should be sensitive to these neuromodulatory changes.
Control for session order effects on task performance, subjective effort.	Effects of session order on accuracy (d') and reaction times in working memory task, on	Session order will be included as a covariate in all analyses since participants improve discrimination accuracy and response	Practice improves performance, and people find tasks with which they have more practice

OBJECTIVES	ENDPOINTS	JUSTIFICATION FOR ENDPOINTS	PUTATIVE MECHANISMS OF ACTION
	discounting of rewards as a function of subjective effort.	speed across sessions with the working memory task. In turn, they find tasks to be less effortful across sessions.	to be subjectively easier.
Tertiary/Exploratory			

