9.4 STATISTICAL ANALYSES

9.4.1 GENERAL APPROACH

There are no categorical outcomes. Key measures are all continuous outcomes, and are described in detail in the next section. They will be analyzed according to pre- versus post-stimulation means. We will also report standard errors for each outcome. Key outcomes have multiple associated measures. Multiple measures will be used to assess reliability by parallel forms.

We will use standard frequentist cut-offs of $p < 0.05$ for all statistical tests, correcting for multiple comparisons. Key t-tests will include pre-post distinctions in E/I balance measures, working memory performance measures, and measures of criticality.

Covariates of no interest to be included are sex and age which we will incorporate via multiple regression to ask whether cTBS alters key outcomes (described in the next session).

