9.4.2 ANALYSIS OF THE PRIMARY ENDPOINT(S)

The following key outcomes will be assessed in this study. All measures are interval with the exception of the categorical covariate of sex.

- Subjective effort
 - Likert scale ratings (ranging from 1-10) of task-induced effort, demand, time pressure, and stress
 - subjective values as estimated from an indifference point discounting procedure
 - self-reported motivation to engage in demanding tasks on a set of Likert scales with continuous values ranging from 0-20
- E/I balance
 - fEI derived measure with exponents ranging approximately from 0.0-2.0
 - power-law exponents with exponents approximating -2.0
- Critical dynamics
 - Long range temporal correlations – a derived measure with exponents ranging approximately from 0.5-1.0
 - Avalanche size and duration distribution exponents approximating -2.0 and -1.5, respectively
- N-back working memory performance
 - overall accuracy rate as a percentage
 - median correct reaction times by trial type: lures versus targets versus regular trials
 - the discrimination index d'

Primary analyses of these outcomes will entail multiple regression models in which outcomes will be regressed on cTBS condition (target versus sham), controlling for sex and age.

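### The EEG hypotheses are tested against pre-stimulation rest only by uncontrolled pre-post t-tests, and the controlled model in 9.4.2 writes no baseline, participant term, channels or session order

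*Protocol*

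**What the plan says.** **Hypotheses.** Section 9.1 states both EEG predictions against the participant's own resting baseline. For criticality it predicts "relative to pre-stimulation rest, cTBS will result in a reduction in markers of critical dynamics". For fE/I it predicts a local reduction "as reflected in the functional E/I balance in proximity to stimulated targets". Of the predictions in 9.1, only the one on subjective effort names angular gyrus stimulation as comparator. The first primary objective in section 3 is likewise general: "Test whether continuous theta-bursts stimulation induces sub-critical dynamics in the cortex".

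**Tests.** Section 9.4.1 says of the key measures: "They will be analyzed according to pre- versus post-stimulation means". It adds: "Key t-tests will include pre-post distinctions in E/I balance measures, working memory performance measures, and measures of criticality". Section 9.4.2 lists the fE/I, long-range temporal correlation and avalanche measures among its outcomes, and defines the primary analysis as multiple regression in which "outcomes will be regressed on cTBS condition (target versus sham), controlling for sex and age". What it calls sham is active cTBS to the angular gyrus (sections 4.1 and 6.1.1).

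**Channels.** EEG is recorded from 64 channels throughout the stimulation session (section 8.1). Apart from the wording in 9.1, the only indication of which channels count is the fE/I row in section 3, which expects a change to be "apparent in the EEG dynamics and thereby the fE/I of channels near the stimulation site".

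**Elsewhere.** Section 4.1 twice makes session order a covariate in all analyses, and 6.3 does so again. Section 9 opens by saying that no formal SAP will be written, so the protocol does not defer these points to one.

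**The concern.** A pre-post comparison within one session picks up whatever changes over that session: fatigue, drowsiness, time in the chair, electrode drift, and cTBS. It cannot tell them apart. The design contains a remedy, because every participant has a second session with the same timeline and a different stimulation site. Section 9 does not put the two parts together. The test that uses the pre-stimulation recording has no control, and the model that has a control does not write the pre-stimulation recording.

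The first primary objective and the fE/I hypothesis are at stake. The working memory and effort objectives already name the angular gyrus comparator. If the outcome form and the channels are settled after the EEG data are seen, that choice could affect the conclusion.

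**Working it through.** **1. What each section fixes for the EEG outcomes.**

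| Section | Comparison | Pre-stimulation value | Control | Channels | Session order |
|---|---|---|---|---|---|
| 9.1 | post vs pre-stimulation rest | yes | none | near the stimulated sites, not listed | not mentioned |
| 9.4.1 t-tests | post vs pre | yes | none | not given | not mentioned |
| 9.4.2 model | dlPFC vs angular gyrus session | not written | yes | not given | omitted |
| 4.1 | dlPFC vs angular gyrus session | – | yes | – | required in all analyses |

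**2. The plan's own figure.** Section 9.2 gives 80% power at d = 0.53 with 30 participants. For a paired, two-sided t-test at 0.05, the noncentrality is 0.53 × √30 = 2.903 and the critical value on 29 df is 2.045, giving power of 80.1%. The figure reproduces, but it concerns N-back performance. The protocol gives no effect size, SD or power for any EEG measure, so the EEG inputs below are assumptions.

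**3. Pre-post t-test with no cTBS effect.** Let δ be the within-session drift in SDs of the change score. The noncentrality is δ√30.

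| δ | δ√30 | Rejection, two-sided 0.05 |
|---|---|---|
| 0 | 0 | 5.0% |
| 0.1 | 0.548 | 8.3% |
| 0.2 | 1.095 | 18.5% |
| 0.3 | 1.643 | 35.5% |
| 0.5 | 2.739 | 75.4% |

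These count as the predicted fall only if drift is downward. With upward drift of 0.2 SD, a significant fall occurs in about 0.1% of trials.

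The protocol does not time the resting recordings. Two 40-second trains 5 to 25 minutes apart (section 4.1) put at least 80 s + 5 min = 6.3 minutes, and up to 80 s + 25 min = 26.3 minutes, between a recording before the first train and one after the second. Section 2.3.1 gives the break as 5 to 15 minutes, and the two passages need to be reconciled.

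**4. Controlled contrast under the same drift.** If both sessions share drift δ, and cTBS effects on the change are τ_D (dlPFC session) and τ_A (angular gyrus session), then (δ + τ_D) − (δ + τ_A) = τ_D − τ_A, so drift cancels. Simulated rejection with no cTBS effect and equal drift of 0.2 or 0.5 SD was 4.8% to 5.0% (40,000 runs, order-adjusted, 15 participants per order).

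**5. Price of the control.** With between-session correlation ρ of the changes, an effect of 0.53 SD of one change score becomes dz = 0.53/√(2(1 − ρ)). Session order uses one further df, leaving 28.

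| ρ | dz | Power, n = 30, two-sided 0.05 |
|---|---|---|
| 0 | 0.375 | 50.9% |
| 0.25 | 0.433 | 62.9% |
| 0.5 | 0.530 | 80.0% |

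The uncontrolled pre-post test has 80.1% at the same effect.

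**6. What the baseline adds to the contrast.** Let r_b be the between-session and r_w the within-session correlation, with unit variances. The between-session difference in post values has variance v = 2(1 − r_b), and its covariance with the difference in pre values is c = 2(r_w − r_b). Adjusting for the pre value leaves v − c²/v. With r_b = 0.5 and r_w = 0.8, v = 1.0, c = 0.6 and the adjusted variance is 0.64, a ratio of 1.56. Over the assumed pairs tried (r_b 0.4 to 0.7, r_w 0.5 to 0.8) the ratio ran from 1.00 to 1.56. Where the unadjusted contrast has 80% power, adjustment gives 80% to 94%.

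**The case against.** The strongest reply is that the protocol already has a controlled EEG analysis. Section 9.4.2 calls the condition regression primary for all listed outcomes, EEG included, and 6.1.1 commits to the dlPFC versus angular gyrus contrast. This stands: a reader might infer that the EEG hypotheses rest on uncontrolled tests alone, and the text does not support that. The fault is that the controlled model is incompletely written.

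Next, 9.4.1 speaks of pre- and post-stimulation means for the very measures that 9.4.2 lists, and 9.4.8 reports both values. Change is therefore the more natural reading of the 9.4.2 outcome. A reader might instead take it as raw post values at channels that follow the coil, so that frontal would be compared with parietal channels and a regional difference could pass for a cTBS effect. The documents do not establish either premise. Section 6.1.1 places the expected change in the dlPFC, while 9.1 and the fE/I row of section 3 speak of stimulated sites generally. What remains is that 9.4.2 states neither the outcome form nor the channels.

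Third, the two tests are complementary. Both sessions are active cTBS, so the site contrast is expected to be zero if cTBS acts equally at both sites, and only the pre-post test can show such a fall. This also stands, and it is why the t-tests should be kept. Rewording 9.1 around the site contrast would replace the sponsor's question, at a power cost that statisticians could reasonably dispute.

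Finally, the size and direction of drift are assumed. At 0.1 SD the excess is small, and nothing in the protocol shows that drift is downward.

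**Conclusion.** The point holds as a defect in how the EEG analysis is written. A pre-post fall from the 9.4.1 t-tests cannot by itself be attributed to cTBS, and the 9.4.2 model that could support attribution lacks a stated pre-stimulation value, participant term, channel set and the session order required elsewhere.

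The 8% to 75% range shows sensitivity to an assumed drift of 0.1 to 0.5 SD of change. It is not an estimate of this trial's error rate. The contrast's near-nominal 5% assumes that drift is the same in both sessions. Its power figures assume 0.53 SD of one change score, borrowed from the N-back calculation, and correlations of 0 to 0.5.

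The textual gap is certain and its numerical effect is not. It should be fixed because it touches the first primary objective and the pre-stimulation data should already be available.

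**What to change.** In 9.4.2, write the EEG condition contrast in full:

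- **Outcome:** the post-stimulation value adjusted for the same session's pre-stimulation value, or the between-session difference in pre-to-post change. Name one.
- **Terms:** condition (dlPFC versus angular gyrus cTBS), participant effect and session order, with sex and age as already planned.
- **Channels:** one left dlPFC cluster, listed in advance and used in both sessions. Report the same contrast at a fixed angular gyrus cluster as supportive.

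Keep the 9.1 hypotheses and the 9.4.1 pre-post t-tests. Add a statement that a pre-post fall alone is not evidence of a cTBS effect, and that attribution to dlPFC cTBS rests on the controlled contrast.

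**Cost.** Text only: EEG runs throughout both stimulation sessions, and pre and post values are already to be reported. The price is the lower precision shown above. On the change-score form, 80% power at the assumed 0.53 SD would take 58, 44 or 30 participants for a correlation of 0, 0.25 or 0.5. Because both sessions are active cTBS, the contrast cannot show an effect that is equal at both sites, and the report should say so.
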